**Aim 1. To determine amphetamine-induced DA release in nonsmokers and in tobacco smokers during acute and prolonged withdrawal.** We will scan 50 Healthy Smokers and 50

Non Smoker healthy controls. Each tobacco smoking subject will participate in up to 4 [C]PHNO PET scans, one pair of scans during the first 2 weeks of smoking abstinence and, for those who remain abstinent, the option to have another pair of scans at 2-8 weeks abstinence. We aim to have at least one week in between sets of scans. Ideally, two PET scans will be carried out in the same day. We first obtain a baseline scan, then approximately three hours before the second scan, amphetamine (0.5 mg/kg, PO) will be administered. Nonsmokers will only be asked to participate in one set of scans. We hypothesize that smokers at 1-2 weeks of withdrawal will have amphetamine-induced DA release that is blunted compared to healthy nonsmokers. We also hypothesize that the smokers who are scanned again at 2-8 weeks withdrawal will exhibit some ‘normalization’ of the dopamine system and will have a larger amphetamine-induced DA release compared to their first scan. We hypothesize that smokers with amphetamine-induced DA release similar to nonsmokers, or that increases over time, will have better abstinence outcomes.

2. **Background:** Describe the background information that led to the plan for this project. Provide references to support the expectation of obtaining useful scientific data.

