**Imaging amphetamine-induced DA release in smokers vs. nonsmokers measured with [C]PHNO and PET.** Amphetamine administration results in a reliable and robust increase in extracellular DA and has been widely used in brain imaging studies as a marker of DA function in psychiatric and healthy populations(8, 9, 12-16). We have chosen oral amphetamine based on its robust and reliable DA signal and because it is routinely used in PET studies(17-23) and by our group to probe DA neurotransmission. The amphetamine robustly increases synaptic levels of DA. The increased DA competes with the radiotracer to bind at the DA receptor, thus an increase in DA results in a decrease in radiotracer binding compared to baseline. This allows calculation of the “occupancy” of the receptors by DA or a change in binding potential (BP), and is an indirect measure of DA release based on the “occupancy model”(13). We have obtained preliminary data that demonstrates blunted DA release in smokers at 2-3 weeks of abstinence vs. controls and is similar to what has previously been found in cocaine- and alcohol- dependent individuals(8, 9). While the previous studies(8, 9) used [C]raclopride which measures striatal D2/3 receptor binding, we propose to use [C]PHNO which measures striatal and extrastriatal (substantia nigra and globus pallidum) D2/3 binding(24). Importantly, blunted DA release in cocaine-dependent individuals was associated with the choice to self-administer cocaine over money(8) and with treatment failure(10). In the current study, we will determine whether smokers have blunted DA release compared to nonsmokers and if the degree of DA release in smokers is associated with time to relapse.

**3. Research Plan:** Summarize the study design and research procedures using non-technical language that can be readily understood by someone outside the discipline. Be sure to distinguish between standard of care vs. research procedures when applicable, and include any flowcharts of visits specifying their individual times and lengths.

**3.1 Overall plan for Aim 1: To determine amphetamine-induced DA release in nonsmokers and tobacco smokers during acute and prolonged nicotine withdrawal.** We will image up to 50 smokers and 40 nonsmokers.

**Smoker-subjects:** Subjects that qualify for the study will be asked to participate in the following:

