- a) One MRI scan, which will take approximately 30-60 minutes. This will take place at the Anlyan Center at [name].
- b) Up to 8 weeks of smoking abstinence- meet with staff multiple times a week to ensure abstinence. For the first week the subject will meet with staff every day (barring an unforeseen circumstance that prevents the subject from meeting). Meetings will occur either at [name], the Yale PET center, or a meeting point midway between the subject and Yale due to distance. As the weeks proceed, meetings will taper down.
- c) Two sets of two PET scans with [C]PHNO approximately 1-2 weeks after quitting smoking and again at 2-8 weeks with at least a week break in between scan sets. Both scans of each set will take about 2 hours each and should be done on the same day. Starting up to 3 hours prior to the second [C]PHNO scan of the set, subjects will be asked to take a drug called amphetamine by mouth. These will take place at the Yale PET Center.

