#### Sequence of procedures

Order	Study procedure	How Long	When
1.	MRI scan/Day 0 appointment: This includes, mri, computer testing, cold pressor task, and withdrawal guidelines.	2 hours	After screening
2.	Smoking abstinence for about 2-8 weeks w/ daily appts for the first week tapering down as the weeks proceed..	2-8 weeks	After MRI scan
3.	Set of 2 PHNO PET scans with amphetamine challenge (with computer task and cold pressor task)	All Day	At ~1-2 weeks of smoking abstinence
4.	MRI scan(with possible computer task and Cold pressor task)	1 hour	At ~ 2-8 weeks of smoking abstinence
5.	Set of 2 PHNO PET scans with amphetamine challenge (with computer task and cold pressor task)	All Day	At ~2-8 weeks of smoking abstinence
6.	May be called followed up with Monthly to check in on smoking status	15 mins	monthly

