Regional [ $^{11}\text{C}$ ]PHNO uptake for each subject will be quantified as  $\text{BP}_{\text{ND}}$  described above for each ROI and will represent the primary outcome measure for the proposed experiments. Repeated measures ANOVA will be used to evaluate the change between scans ( $\Delta\text{BP}$ ) for brain measures for the scans.  $\Delta\text{BP}$  will be computed as  $[(\text{BP}_{\text{baseline}} - \text{BP}_{\text{condition}}) / \text{BP}_{\text{baseline}} \times 100]$ . Analysis will be conducted using SAS version 9.1 (Cary, NC).  $N=20$  subjects per group is necessary to detect differences between smokers and nonsmokers. Potential associations, e.g., relationship between magnitude of dopamine release and time to relapse, will be examined using correlation analysis with Type I error corrected for multiple comparisons. Exploratory analyses of the other cognitive and behavioral measures and their relationship to relapse will also be performed.

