### 3.8 Contingency Reinforcement for Smoking Cessation (for healthy smokers)

We plan to image smokers during the first 8 weeks of abstinence. Contingency management techniques have been successfully used to help smokers quit smoking by a number of investigators including our group for many years (34-36).

We will help the subjects set a quit date and prior to the quit date they will meet with the research staff who will provide them with brief advice on quitting smoking based on AHCPR guidelines (The Smoking Cessation and Clinical Practice Guideline Panel and Staff, 1996). They will be advised about the risks and benefits of quitting smoking and told that they will be monitored daily to ensure abstinence. Subjects will be informed of payment schedules (see below) for CO levels indicating abstinence and also given information on how quit rates in the first week of smoking cessation predicted sustained abstinence. We use CO levels < 11 ppm to define abstinence from cigarettes. During the first week of abstinence we will obtain CO levels during contingency management meetings from subjects up to twice daily. In addition, we will obtain urine samples once daily to measure cotinine levels (a nicotine metabolite). These meeting will occur either in the research office, the Yale PET center, or in a midway point if subjects travel a far distance.

For each contingency management appointment, subjects will get \$10 if their CO levels are less than 1 ppm and urine cotinine levels are less than 100 ng/ml.

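### PHNO protocol: relapse is seen only at contacts that thin out and may not happen, yet time to relapse is to be analysed by a correlation that allows for no censoring

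*Combined protocol and SAP*

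**What the plan says.** All references are to the PHNO protocol, the second protocol in the combined document.

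- **Question.** The Background section will determine "if the degree of DA release in smokers is associated with time to relapse". Aim 1 adds that smokers whose DA release is like that of nonsmokers, or rises over time, "will have better abstinence outcomes".
- **Week 1.** Section 3.1, smoker item b: "For the first week the subject will meet with staff every day". Section 3.8: "During the first week of abstinence we will obtain CO levels during contingency management meetings from subjects up to twice daily", plus one urine cotinine sample a day.
- **After week 1.** Item b: "As the weeks proceed, meetings will taper down". No intervals are given, although the same item speaks of several meetings a week over up to 8 weeks. The Sequence of procedures table for smokers gives this phase as about 2 to 8 weeks.
- **Later.** The last row of that table: "May be called followed up with Monthly to check in on smoking status". No biochemical check and no end date are stated. Section 7 makes willingness to be contacted monthly by phone or email an inclusion criterion.
- **Scans.** The first set is at about 1 to 2 weeks of abstinence. The second, at 2 to 8 weeks, is optional and only for smokers still abstinent (Aim 1).
- **Analysis.** Section 3.7, repeated in section 11: "relationship between magnitude of dopamine release and time to relapse, will be examined using correlation analysis with Type I error corrected for multiple comparisons".

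No passage says how a relapse is dated, fixes a common length of follow-up, or says what is entered for a smoker who has not been seen to relapse.

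**The concern.** A correlation needs one number per smoker. The contact plan cannot supply it, for two reasons.

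1. Unless a date is asked for, relapse is known only to lie between the last contact showing abstinence and the first showing smoking. That gap is a day in week 1, an unstated length during the taper, and a month or more afterwards.
2. A smoker last seen abstinent has no relapse time. Dropping such smokers removes those who did best. Entering the last contact date as a relapse replaces the outcome with length of follow-up.

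DA release is first measured at 1 to 2 weeks. The relapse time it could predict therefore falls mostly or wholly after the densely observed week. At stake is the relapse association, a stated question of the study. If follow-up length varies between smokers, the recorded correlation can shrink; if that length is also related to DA release, a correlation can appear where none exists.

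**Working it through.** **Plan's own figure.** There is none to reproduce. No sample size, event count or power is given for time to relapse.

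**Assumptions.** The taper is unspecified, so two versions were tried. After daily contact to day 7:

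- Taper A: every 2 days to day 28, then every 3 days to day 56.
- Taper B: every 2 days to day 14, every 3.5 days to day 28, then weekly to day 56.

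Each was compared with in-person contact ending at day 14 (last visit day 13). Calls, where made, come every 30 days after the in-person phase ends.

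**Step 1: what is known about a relapse on day 20.5.**

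| Contact | Relapse known to lie between |
|---|---|
| Taper A to day 56 | days 19 and 21 |
| Taper B to day 56 | days 20 and 23.5 |
| Visits to day 14, then calls | days 13 and 44 |
| Visits to day 14, no calls | after day 13 only (right-censored) |

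**Step 2: mean lag from relapse to the next contact.** For relapse spread evenly over a gap of *s* days, the mean lag is *s*/2. In week 1 it is 0.5 day. For relapse on days 14 to 56 (42 days), each term is days in the stretch × mean lag:

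- Taper A: (1×0.5 + 12×1 + 27×1.5 + 2×31)/42 = 115/42 = 2.7 days. Of the 115, 62 comes from the last two days, which wait for the call on day 86.
- Taper B: (2.5×1.25 + 10.5×1.75 + 28×3.5 + 1×30.5)/42 = 150/42 = 3.6 days.
- Visits to day 14, calls on days 44 and 74: (30×15 + 12×24)/42 = 738/42 = 17.6 days.

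**Step 3: effect on the correlation.** The simulation used 50 smokers, 1,000 runs per row and taper B. Relapse fell at day 14 plus an exponential time with median 30 days. It was recorded at the first contact at or after it happened; if never seen, the last contact was entered. Some smokers stay on visits to day 56 and the rest stop at day 14. Calls, if made, run to day 180. Entries are the mean recorded Spearman correlation and the share of runs with p<0.05.

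| True correlation | Share kept on visits to day 56 | Calls made | No calls |
|---|---|---|---|
| 0.38 | 50%, unrelated to DA release | 0.34 (69%) | 0.08 (9%) |
| 0 | 50%, unrelated | 0.00 (4.5%) | 0.00 (4.7%) |
| 0 | 70% high / 30% low DA release | -0.06 (9%) | 0.31 (61%) |

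With calls made, the order of relapse times is largely kept. Without calls, every smoker leaving visits at day 14 gets the same recorded day, so the record mainly reflects who stayed on visits.

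**The case against.** Several counter-arguments have force.

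- **Visits may stay frequent.** Item b mentions several meetings a week, and section 3.8 tells subjects that they will be monitored daily. In a model with relapse exponential (mean 40 days) after a day-10 scan, counting relapses before day 56, two visits a week to day 56 give a mean delay of 1.7 days. A schedule thinning to weekly gives 3.0. This stands: while visits last, the lag is small.
- **Delay is not the same as bias.** When calls are always made, the correlation barely moves (0.38 to 0.34). This stands too. The large distortions require missing calls and unseen relapse entered at last contact; the spurious one also requires retention related to DA release.
- **Staff could ask for a date, and willingness for monthly contact is an entry criterion.** Both are possible, but the plan commits to neither. Willingness is not a schedule, and the table says only that contact may take place.
- **The relapse analysis is secondary.** It is introduced as a potential association and has no power claim. This limits the reach of the point.

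A reader might infer something stronger: that smokers taking the second scan set are by design watched to week 8 while the others move to calls at about week 2, biasing recorded relapse by about 13 days (16.0 minus 3.0 in the model above). The documents do not support this. Section 3.1 lists abstinence visits (item b) separately from scans (item c), and nothing ends visits for a smoker who declines the second set. That set is also open only to those still abstinent. In the same model, 53% of relapses before day 56 occur before day 28 and 81% before day 42, so a second set on those dates would come too late for them. What remains is that a phase of 2 to 8 weeks with an optional second set does not guarantee equal follow-up.

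**Conclusion.** The point holds for the relapse association only. From the text alone, relapse is observed only at contacts; their spacing goes from daily to an unstated taper to possible monthly contact; and the planned correlation provides neither for interval-known dates nor for smokers last seen abstinent.

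The size is conditional. It is small if every call is made and smokers are followed to relapse. It can be large if calls are missed: 0.38 falling to 0.08, or a spurious 0.31 with 61% of runs at p<0.05 when retention on visits also depends on DA release. These figures rest on assumed taper dates, relapse rate, retention and handling of unseen relapse, none of which the documents give. In the simulation retention is also independent of relapse, whereas the real second set is restricted to abstainers.

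Unequal follow-up by second-set choice is a possibility the plan leaves open; the plan does not state it. The primary comparison of DA release between smokers and nonsmokers is unaffected. This is a cheap improvement worth making, since dates not asked for at the time cannot be reliably recovered later.

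**What to change.** 1. **Analysis (sections 3.7 and 11).** Replace the correlation for time to relapse with a time-to-event model having DA release as the predictor and time counted from the first scan set. Right-censor smokers at the last contact at which they were known to be abstinent. Use interval censoring where relapse is known only to lie between two contacts.
2. **Data collection.** At every existing visit and call, ask for and record the date of the first cigarette since the last contact.
3. **Follow-up (section 3.1 and the Sequence of procedures table).** Make monthly contact planned, with a stated end date, for every scanned smoker whether or not the second set is taken.
4. **Sensitivity analysis.** Report relapse known only from self-report separately from relapse found at verified visits.

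**Cost.** One extra question per contact, calls that are always made, and slightly wider confidence intervals because uncertainty in the date is now shown. No scan or visit is added.

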#### Sequence of procedures

Order	Study procedure	How Long	When
1.	MRI scan/Day 0 appointment: This includes, mri, computer testing, cold pressor task, and withdrawal guidelines.	2 hours	After screening
2.	Smoking abstinence for about 2-8 weeks w/ daily appts for the first week tapering down as the weeks proceed..	2-8 weeks	After MRI scan
3.	Set of 2 PHNO PET scans with amphetamine challenge (with computer task and cold pressor task)	All Day	At ~1-2 weeks of smoking abstinence
4.	MRI scan(with possible computer task and Cold pressor task)	1 hour	At ~ 2-8 weeks of smoking abstinence
5.	Set of 2 PHNO PET scans with amphetamine challenge (with computer task and cold pressor task)	All Day	At ~2-8 weeks of smoking abstinence
6.	May be called followed up with Monthly to check in on smoking status	15 mins	monthly

#### *Non-Smoker subjects:*

Subjects that qualify for this study will be asked to participate in the following:

- a) One MRI scan, which will take approximately 30-60 minutes. This will take place at the Anlyan Center at [name].
- b) One set of two PET scans with [C]PHNO. Both scans of the set will take about 2 hours each and should be done on the same day. Starting up to 3 hours prior to the second [C]PHNO scan of the set, subjects will be asked to take a drug called amphetamine by mouth. This will take place at the Yale PET Center.

#### Sequence of procedures

Order	Study procedure	How Long	When
1.	MRI scan/Day 0 appointment(with computer task and cold pressor task)	2 hours	After screening
2.	Set of 2 PHNO PET scans with amphetamine challenge(with computer task and cold pressor task)	All Day	After screening

### 3.2 Subject recruitment.

We have an established program to recruit healthy controls. For the present study, subjects will be recruited through our program as well as flyers, public advertisement (newspaper, radio, internet postings), and word of mouth.

### 3.3 Screening for eligibility.

After completing the informed consent process, subjects will have a physical and neurological examination. The following lab tests will be performed at screening to exclude medical illnesses: complete blood count (CBC) and differential, chemistries, kidney function tests (creatinine, BUN, urinalysis), liver function tests, and TSH. A urine drug screen and a pregnancy test (for women) will be done at screening and before radiotracer administration on each PET scan day. The psychiatric assessment will include a psychiatric history, a structured clinical interview (SCID), and assessment of subsyndromal depression with the Center for Epidemiological Studies Depression Scan – CES-D and subsyndromal anxiety with Spielberger State-Trait Inventory (STAI).

#### Aim 1 Healthy nonsmokers

- smoked < 100 cigarettes in lifetime
- urinary cotinine levels 0-30 ng/mL both at intake evaluation and on scan day

#### Aims 1 Healthy Smokers

- have been smoking cigarettes on a daily basis for at least 1 year
- carbon monoxide levels > 8 ppm during intake evaluation
- plasma nicotine levels > 10 ng/mL during intake evaluation
- plasma cotinine levels of > 50 ng/mL during intake evaluation
- wish or willing to quit smoking for at least 1 week and up to 8 weeks

### 3.4 Assessments:

All participants will be screened initially using a telephone screen that will include questions to evaluate medical history, personal and familial psychiatric and smoking history.

#### 3.4a. General Intake Assessments

1. Demographic Questionnaire This questionnaire will obtain: (1) basic demographic information including age, gender, marital status, employment status, occupation, (2)

alcohol/drug history, (3) family history of alcohol/drug use, depression, anxiety, and smoking history.

2. Medical History This questionnaire will obtain a basic medical history (personal and family) including past or current conditions such as neurological, endocrine, cardiovascular, renal, liver, and thyroid pathology. Current body weight and current medications will also be assessed.

3. Medical Assessments will include a physical exam by a state licensed physician (overseen by [name]), a complete blood count, blood urea nitrogen, creatinine, fasting blood sugar, electrolytes, liver function tests, thyroid function tests (including T3, T4, T3RU, estimated free T4), thyroid stimulating hormone levels, urine toxicology, EKG, and urinalysis. Female subjects will have serum pregnancy tests. All EKGs are read by a state licensed cardiologist and all abnormal MRIs will be reviewed by a state licensed neuroradiologist.

4. Illicit Drug/Pregnancy Screen A urine sample will be collected to determine current illicit drug use (for all potential subjects), positive results other than THC may be cause for exclusion from the study, however positive results will not be kept on file due to the sensitive nature of this information. In addition, urine samples will be collected for the intake visit and on each MR and PET scan day to confirm that the subject is not pregnant. Note: the urine pregnancy test will not be required prior to the MRI if the serum pregnancy test was done within 1 week prior to the MR imaging session.

5. Structured Clinical Interview for DSM-IV Axis I Disorders The psychotic screening and depression sections of the Structured Clinical Interview for DSM-IV Axis I Disorders (SCID) will be used to determine whether subjects meet exclusion criteria for diagnosis of psychotic disorders and major depression (25).

### 3.4b. Mood Measures

We may of mood and anxiety at intake and also on the PET scan day including the following.

1. Center for Epidemiological Studies Depression Scale (CES-D) The CES-D (26) is a 20-item self-report instrument, which has been extensively used in both clinical and nonclinical populations to measure the frequency and severity of depressive symptoms over the past week. The CES-D, which has been used to document the severity of depressive symptoms in adults (27) and has been shown to be a sensitive measure of negative affect in smokers (28), will be used in the proposed studies to exclude for presence of major depression, and to measure level of mild depressive symptoms commonly noted in tobacco smokers.

2. Anxiety: The State-Trait Anxiety Inventory (29) is a 40-item, self-report measure, comprised of two subscales. The State-Anxiety scale is 20 items and assesses transitory states characterized by feelings of tension, apprehension, and heightened autonomic reactivity. The Trait-Anxiety scale is 20 items and assesses stable individual differences in anxiety proneness.

3. Impulsivity: Barratt Impulsiveness Scale (BIS; (30)) is a 30 item self-report instrument designed to assess the personality/behavioral construct of impulsiveness.

